2.14 Interim analysis

No interim analysis is planned.

3 Sample size calculation

In CHOIR (Mitchell 2002), treatment with Omapatrilat was associated with an approximately ~10% reduction in characteristic impedance at 12 weeks, with little or no change seen amongst enalapril- treated patients. Based on a similar study design and population, and accounting for a dropout rate of 20% from first visit to subsequent follow up and a 10% rate of non-evaluable data, assuming a standard deviation of 80 for the primary efficacy variable and 90% power, a sample size of 432 patients (216 per arm) will be necessary to detect a clinically important change of 30 dyne x sec/cm⁵ between the two treatment groups.

Assuming a significance level of 0.05, a sample size 432 patients would provide 88% power to detect a 25% reduction in the geometric mean of the proportional change from baseline to Week 12 in NT-proBNP for the sacubitril and valsartan treatment group assuming a value of 0.95 for the enalapril group, a value of 0.7125 for the sacubitril and valsartan group (25% reduction), a common standard deviation of 0.85 and a 20% drop-out rate. The difference between the logs for the two treatment groups is therefore assumed to be 0.288.

4 Change to protocol specified analyses

The following changes to protocol specified analyses were made:

- Modified baseline definition as follows:
 - Eliminated requirement that assessment date:time is prior to first dose date:time
 - Clarified how baseline assessments for hemodynamic variables will be identified
- Clarified that tables summarizing demographics and baseline data will be run only on the FAS, and not also on the RS as indicated in the protocol
- Indicated that values of the hemodynamic variable carotid-femoral pulse wave velocity will be negative inverse transformed prior to analysis
- Added separate summaries of prior and concomitant CV, HF, ACEi and ARB medications
- Added the following supportive analyses of the primary endpoint:
 - On-treatment analysis

- Analysis using the “original” aortic characteristic impedance variable
- Analysis using the “alternative” aortic characteristic impedance variable
- Added on-treatment analyses of the secondary endpoints
- Modified the PPS definition to clarify that major protocol deviations will exclude patients from the PPS regardless of the study phase in which they occur
- Added summary of the incidence of hypotension through Week 12
- Added separate summaries of the incidence of hyperkalemia and worsening renal function through Week 12 based on central laboratory data
- Added summary of positively adjudicated angioedema
- Removed CPK from the list of notable chemistry abnormalities since this safety lab was not performed for the study
- Except for the Study Objectives and Endpoints section (to maintain consistency with the corresponding protocol objectives wording), references to "Carotid pressure-flow + pulsatility index" were replaced by "Aorta-carotid reflection coefficient and carotid pulsatility index" as it is a more accurate description
- Clarified that BNP samples will be re-assayed using EDTA tubes for purposes of a side-by-side comparison of results where the value and change from baseline at each visit will be summarized for the subset of patients who have change from baseline values for the 2 BNP assays at the given visit

5 Appendix

5.1 Imputation rules

5.1.1 Study treatment

Full dates for study treatment collected on the eCRF are required; therefore, no imputations will be made.

5.1.2 AE date imputation

The following algorithm should be used to estimate start dates for which only partial information is known:

- Missing day and month
 - If the year is the same as the year of first study treatment, then the day and month of the start date of treatment will be assigned to the missing fields.
 - If the year is prior to the year of first study treatment, then December 31 will be assigned to the missing fields.
 - If the year is after the year of first study treatment, then January 1 will be assigned to the missing fields.

- Missing month only
 - Treat day as missing and replace both month and day according to the above procedure.
- Missing day only
 - If the month and year are the same as the year and month of first study treatment, then the start date of treatment will be assigned to the missing day.
 - If the month and year are before the year and month of first study treatment, then the last day of the month will be assigned to the missing day.
 - If the month and year are after the year and month of first study treatment, then the first day of the month will be assigned to the missing day.

If the imputed start date result is after the stop date (and the stop date is complete), the imputed start date will be reset to the stop date.

The following algorithm should be used to estimate stop dates for which only partial information is known:

- Missing year
 - Date left missing.
- Missing month
 - Impute 'December'.
- Missing day
 - Impute 'last date of that month'.

5.1.3 Concomitant medication date imputation

The following algorithm should be used to estimate start dates for which only partial information is known:

- Missing day and month
 - If the year is the same as the year of first study treatment, then the day and month of the start date of treatment will be assigned to the missing fields.
 - If the year is prior to the year of first study treatment, then December 31 will be assigned to the missing fields.
 - If the year is after the year of first study treatment, then January 1 will be assigned to the missing fields.
- Missing month only
 - Treat day as missing and replace both month and day according to the above procedure.
- Missing day only

- If the month and year are the same as the year and month of first study treatment, then the start date of treatment will be assigned to the missing day.
- If the month and year are before the year and month of first study treatment, then the last day of the month will be assigned to the missing day.
- If the month and year are after the year and month of first study treatment, then the first day of the month will be assigned to the missing day.

If the imputed start date result is after the stop date (and the stop date is complete), the imputed start date will be reset to the stop date.

The following algorithm should be used to estimate stop dates for which only partial information is known:

- Missing year
 - Date left missing. Consider the medication to have been received at all periods after that period determined by the start date.
- Missing month
 - Impute 'December'.
- Missing day
 - Impute 'last date of that month'.

5.2 AEs coding/grading

The [REDACTED] coding team will code the AE terms using MedDRA v21.1 or later. If any terms are not coded, the data management team will issue queries to sites to update the AE term appropriately.

5.3 Laboratory parameters derivations

5.3.1 Laboratory grading

The collected laboratory values will be summarized by severity (low/normal/high) and not converted to Common Terminology Criteria for Adverse Events (CTCAE) grades.

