### **9.5.2 Safety variables**

The safety and tolerability assessments are listed below:

- AEs and SAEs
- Sitting systolic, diastolic BP, and pulse pressure
- Heart rate
- Laboratory values

The assessment of safety will be based primarily on the frequency of adverse events, SAEs, and laboratory abnormalities. Other safety data will be summarized as appropriate.

The incidence of treatment-emergent adverse events (new or worsened) will be summarized by primary system organ class, preferred term, severity, and relationship to study drug. In addition, the incidence of death, SAEs, and AEs leading to discontinuation will be summarized separately by primary system organ class and preferred term.

Laboratory data will be summarized by presenting shift tables using extended reference ranges (baseline to most extreme post-baseline value), by presenting summary statistics of raw data and change from baseline values (mean, median, standard deviation, 25th and 75th percentiles, interquartile range, minimum and maximum) and by the flagging of notable values in data listings.

[figure not shown]

[figure not shown]
Data from other tests (e.g., vital signs) will be listed, notable values will be flagged, and any other information collected will be listed as appropriate.

Safety analyses will be performed based on the Safety Set. There will be no inferential analyses of the safety data. See [Section 9.5.1](#).

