2.8.3 Laboratory data

Laboratory values will be summarized using shift tables (from baseline to most extreme post baseline value) by each laboratory parameter at its worst severity by study phase (see Section 2.1.1 for study phase phase definitions). The number and percentage of patients with laboratory values will be presented by low/normal/high (low and high) classifications to compare baseline to worst post baseline value. Unscheduled assessments will be considered.

In addition, laboratory values and the change from baseline for each parameter by visit will be summarized by treatment group and open-label sacubitril/valsartan. In the event there are multiple laboratory values within a visit, the worst value will be summarized.

A separate summary table will be presented by study phase (see Section 2.2.1 for study phase phase definitions) with the number and percentage of patients having notable lab abnormalities based on percent change from baseline (see Section 5.3 for a list of notable laboratory abnormalities). Unscheduled assessments will be considered.

Listings of all laboratory values will be provided. A separate listing for pregnancy tests will also be provided. Any notable laboratory abnormalities will be flagged.

Laboratory values indicated as $<x$ will be converted to $(0.5)(x)$ for purposes of analysis. Laboratory values indicated as $>x$ will be converted to the values specified in the below table for purposes of analysis.

Laboratory Test	Unconverted Value	Converted Value for Analysis
Red Blood Cell Count	>7.00	7.1
Potassium	>7.0	7.1
Urine Erythrocytes	>182	182.1
Urine Leukocytes	>182	182.1

The incidence of hyperkalemia through Week 12 will be calculated by treatment group. The relative risk (sacubitril/valsartan vs. enalapril) and 95% confidence interval will be presented. Hyperkalemia will be determined from the central laboratory data as potassium >5.3 mEq/L. Unscheduled assessments will be considered.

Similarly, the incidence of worsening renal function through Week 12, relative risk (sacubitril/valsartan vs. enalapril) and 95% confidence interval will be presented. Worsening renal function will be determined from the central laboratory data as a worsening (decrease) in eGFR of $\geq 35\%$ from baseline, or an increase in creatinine of ≥ 0.5 mg/dL from baseline and a worsening (decrease) in eGFR of $\geq 25\%$ from baseline. Unscheduled assessments will be considered.

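### The SAP builds laboratory shift tables on low/normal/high where the protocol specifies extended reference ranges, does not declare the change, and leaves no graded count of absolute excursions for potassium and seven other chemistry tests

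*SAP*

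**What the plan says.** Protocol 9.5.2 states: "Laboratory data will be summarized by presenting shift tables using extended reference ranges (baseline to most extreme post-baseline value". The same sentence adds descriptive statistics for raw and change-from-baseline values, and flags for notable values in the listings.

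SAP 2.8.3 keeps the shift table from baseline to the most extreme value but changes the scale: "Laboratory values will be summarized using shift tables (from baseline to most extreme post baseline value) by each laboratory parameter at its worst severity". The two study phases are tabulated separately. It then says that the counts "will be presented by low/normal/high (low and high) classifications to compare baseline to worst post baseline value". SAP 5.3.1 confirms the scale, "The collected laboratory values will be summarized by severity (low/normal/high", and rules out conversion to CTCAE grades.

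The SAP also plans, in 2.8.3:

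- by-visit summaries: "laboratory values and the change from baseline for each parameter by visit will be summarized by treatment group";
- a table by study phase of the "number and percentage of patients having notable lab abnormalities based on percent change from baseline", with the criteria in SAP 5.3.2;
- the incidence through Week 12 of hyperkalemia (potassium above 5.3 mEq/L) and of worsening renal function (defined relative to baseline), each with a relative risk and 95% confidence interval;
- listings of all values with notable abnormalities flagged.

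SAP Section 4 lists changes to protocol-specified analyses. It goes down to the removal of CPK from the notable list, but has no entry on extended reference ranges.

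**The concern.** There are two problems.

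The first is an undeclared difference between the documents. The protocol names the type of reference range for the shift tables. The SAP does not say which range defines its categories and does not use the protocol's term. A programmer working from the SAP would probably use the laboratory's ordinary limits, and a reader of Section 4 would not learn that anything had changed.

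The second is what the SAP's table can show. It reports each parameter at its worst severity, but with one abnormal band per side there are no degrees of severity to rank. The added low-and-high category names both directions and adds no degree.

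Protocol 9.5.2 rests the safety assessment mainly on adverse events, SAEs and laboratory abnormalities, so the laboratory tables should let a reader see how many patients in each arm had marked values, as well as how many crossed a limit.

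**Working it through.** The plan states no figure on this point, so there is none to reproduce. The check sets the documents side by side and then passes example values through the SAP's rules.

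**1. Scale of the shift table.**

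| | Protocol 9.5.2 | SAP 2.8.3 and 5.3.1 |
|---|---|---|
| Comparison | baseline to most extreme post-baseline value | the same |
| Categories | extended reference ranges (limits not given) | low, normal, high, and low and high; range not named |
| Declared in SAP Section 4 | – | no |

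**2. What the shift table separates.** The documents give no upper limit of normal for potassium, so I assume 5.0, 5.1 or 5.3 mEq/L.

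- Baseline 4.5, worst value 5.4 or 6.5: normal to high in both cases, at all three limits.
- Baseline 5.2, worst value 5.4, 6.2 or 6.5: all high to high if the limit is 5.0 or 5.1; all normal to high if it is 5.3.

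The table never separates the smaller excursion from the larger one. The same holds for sodium: with any lower limit above 134 mEq/L, values of 134 and 120 are both low.

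**3. Coverage of the notable-change table.** Protocol 6.5.7.2 names 17 chemistry tests besides hemoglobin A1c. SAP 5.3.2 gives a criterion for 10: ALT, AST, BUN, creatinine, total bilirubin, alkaline phosphatase, potassium, chloride, calcium and uric acid. The difference is 17 − 10 = 7: sodium, glucose, magnesium, phosphorus, albumin, total protein and GGT.

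**4. Potassium under the other two rules.** I take 5.2 mEq/L as baseline because Protocol 4.2 excludes values above it at screening. The notable rule is a rise of more than 20%, so the threshold is 1.20 × 5.2 = 6.24. The percent change is 100 × (value / 5.2 − 1).

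| Worst value (mEq/L) | Change from 5.2 | Notable (>20%) | Hyperkalemia (>5.3) |
|---|---|---|---|
| 5.4 | +3.8% | no | yes |
| 6.0 | +15.4% | no | yes |
| 6.2 | +19.2% | no | yes |
| 6.3 | +21.2% | yes | yes |
| 6.5 | +25.0% | yes | yes |

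The hyperkalemia table counts all five rows alike. The notable table separates them by relative change, which is a different quantity: from a baseline of 4.0 the threshold is 1.20 × 4.0 = 4.8, so a rise to 4.9 (+22.5%) is notable while 5.2 to 6.2 is not.

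The window in which a value of 6.0 escapes the notable rule is narrow. It needs 6.0 ≤ 1.20 × baseline, that is, a baseline of at least 6.0 / 1.20 = 5.0.

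**5. The protocol's own bands.** Protocol Appendix 2 divides potassium into above 5.3 to 5.5, above 5.5 to below 6.0, and 6.0 or more. No table in the readable SAP counts patients in the upper two bands.

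**The case against.** The strongest reply is that the shift table is one output among several and that the SAP adds to the protocol elsewhere. The protocol only flags notable values in listings; the SAP counts them by study phase. It also adds incidence tables for hyperkalemia, worsening renal function and hypotension (SAP 2.8.3 and 2.8.4.1), the three major risks named in Protocol 3.6.1. This stands, and it rules out some stronger readings.

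- A reader might infer that patients abnormal at baseline cannot be seen to worsen. That is true only inside the shift table. A creatinine rise from 1.6 to 3.0 mg/dL is 3.0 / 1.6 − 1 = +87.5%. It is counted under the more-than-50% notable rule, and very likely as worsening renal function, since the rise of 1.4 mg/dL exceeds the 0.5 required and the eGFR fall would be large.
- A reader might infer that the shift table is the only categorical view of the seven tests without a criterion. Protocol 6.5.7 and 7.1 require clinically significant laboratory abnormalities to be recorded as adverse events, and SAP 2.8.1 tabulates these by severity. That route depends on the investigator's judgement and does not grade the measured value. The missing criteria also originate in Protocol Appendix 1, which lacks the same seven.
- A reader might infer that chance crossings of normal limits swamp a true difference between arms. Any such figure needs assumed 95% limits and a within-patient correlation that the documents do not give, and SAP 2.8 plans no inferential safety analysis.

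It can also be said that neither document defines extended ranges or their number of levels, that low/normal/high could be applied to extended limits, and that the table shells are a separate document not available here. This is fair, and it means the SAP may not have intended a change. It does not remove the need for the SAP to name its range. Nor does it help with degree, because a single band per side has the same limitation wherever the limit is set.

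**Conclusion.** The point holds in a limited form. The SAP departs, at least in wording, from a laboratory analysis that the protocol specifies, and does not declare it. Inside the shift table, degrees of excursion on one side are not separated, and high-to-high or low-to-low worsening does not show; low/normal/high is therefore not a severity scale.

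Other outputs cover much of the gap. What is left is that no SAP laboratory table counts degrees of absolute excursion for the seven chemistry tests without a notable criterion, or for potassium in the protocol's own upper bands. For potassium, the failure of the percent rule at 6.0 mEq/L is confined to baselines of 5.0 or above, but the lack of a count at 6.0 or more applies to every patient.

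The coverage count and the percent-change arithmetic use only figures in the documents. The shift-cell examples rest on assumed limits of normal, but the failure to separate smaller from larger excursions is the same at every limit tried. The issue is descriptive safety reporting: worth correcting, with no bearing on sample size, power, type I error or the primary result.

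**What to change.** In SAP 2.8.3 and 5.3.1:

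- State which reference range the shift table uses. Restore the protocol's extended reference ranges, define their limits before unblinding, and show them as additional bands beyond low and high.
- Tabulate the worst post-baseline potassium by arm and study phase in the bands that Protocol Appendix 2 already uses. This is for reporting only and implies nothing about management.
- Stop calling low/normal/high a severity scale unless it has graded bands.

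In SAP Section 4, list any departure from Protocol 9.5.2 that remains.

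The cost is SAP wording and table shells; no new data are needed. The drawback is wider tables with some sparse cells.

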5.3.2 Notable laboratory values

Hematology

RBC count	>50% increase, >20% decrease
Hemoglobin	>50% increase, >20% decrease
Hematocrit	>50% increase, >20% decrease
WBC count	>50% increase, >50% decrease
Platelet count	>75% increase, >50% decrease

Blood Chemistry

ALT (SGPT)	>150% increase
AST (SGOT)	>150% increase
BUN	>50% increase
Creatinine	>50% increase
Total bilirubin	>100% increase
Alkaline phosphatase	>100% increase
Potassium	>20% increase, >20% decrease
Chloride	>10% increase, >10% decrease
Calcium	>10% increase, >10% decrease
Uric acid	>50% increase

5.4 Vital signs

5.4.1 Notable vital sign values

Systolic blood pressure	<90 mmHg and decrease of >20 mmHg from baseline >180 mmHg and increase of >20 mmHg from baseline
Diastolic blood pressure	<50 mmHg and decrease of >15 mmHg from baseline >105 mmHg and increase of >15 mmHg from baseline
Pulse	<50 bpm and decrease of > 15 bpm from baseline >120 bpm and increase of >15 bpm from baseline
Weight	>7% decrease; >7% increase

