## **13 Appendix 1: Clinically notable laboratory values and vital signs**

Clinically notable vital signs will be defined in this study as a SBP < 90 mmHg. The study treatment shall be interrupted or stopped based on investigator judgement.

Clinically notable laboratory abnormalities for selected tests based on a percent change from baseline:

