2.1.1 General definitions

Study treatment

Patients will receive either sacubitril/valsartan or enalapril during the first 12 weeks of the study. Study treatment will refer to either of these two drugs.

Baseline

In general, baseline is defined as the last non-missing assessment prior to or on the start date of study treatment (randomization date for patients not treated). For hemodynamic variables baseline is defined as the assessment with a planned time point value of 'Visit_1_Baseline'.

Unscheduled assessments will be excluded from the determination of baseline.

Date of first administration of study treatment

Double-blind phase: The date of first administration of study treatment in the double-blind phase is defined as the first date a dose of study treatment is administered and recorded on the Dosage Administration Record - At Visit (Visit 2) electronic case report form (eCRF).

Open-label phase: The date of first administration of study treatment in the open-label phase is defined as the first date a dose of sacubitril/valsartan is administered in the open-label phase and recorded on the Dosage Administration Record - At Visit (Visit 7) eCRF.

Date of last administration of study treatment

Double-blind phase: The date of last administration of study treatment in the double-blind phase is defined as the last date a dose of study treatment is administered in the double-blind phase and recorded on the Dosage Administration Record - At Visit (Visit 6) eCRF. In the event this date is not available from the Dosage Administration Record - At Visit (Visit 6) eCRF, it will

be determined from the End of Study Treatment eCRF or Dosage Administration Record - Summary eCRF.

Open-label phase: The date of last administration of study treatment in the open-label phase is defined as the last date a dose of sacubitril/valsartan is administered in the open-label phase and recorded on the Dosage Administration Record - Summary eCRF.

The date of last administration of study treatment during the study is defined as the last date a dose of study treatment is administered and recorded on the End of Study Treatment eCRF. In the event this date is not available from the End of Study Treatment eCRF, it will be obtained from the Dosage Administration Record - Summary eCRF.

Study day

The study day describes the day of the assessment relative to the date of randomization.

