2.8.4 Other safety data

2.8.4.1 Vital signs

All vital signs (systolic and diastolic blood pressure [mmHg], pulse rate [beats per minute], respiration rate [breaths per minute], weight [kg], height [cm], and BMI [kg/m²]) will be descriptively summarized at each visit by treatment group and open-label sacubitril/valsartan. Change from baseline will also be presented.

A separate summary table will be presented with the number and percentage of patients having notable vital signs based on changes relative to baseline values (see Section 5.4 for a list of notable vital signs) by study phase (see Section 2.1.1 for study phase definitions). Unscheduled assessments will be considered.

The incidence of hypotension through Week 12 will be calculated by treatment group. The relative risk (sacubitril/valsartan vs. enalapril) and 95% confidence interval will be presented. Hypotension will be determined from the vital signs data as systolic blood pressure <90 mmHg. Unscheduled assessments will be considered.

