5.6 Rule of exclusion criteria of analysis sets

Table 1 Protocol deviations that cause patients to be excluded

Deviation ID	Description of Deviation	Exclusion in Analyses
I03	Patient did not have history of HTN and one of the following at BOTH screening and pre-randomization: a. SBP > 105 mm Hg on antihypertensive medication b. SBP \geq 140 mm Hg and NOT on antihypertensive medication	Exclusion from PPS
I04	Patient was not diagnosed with heart failure NYHA class I-III and reduced ejection fraction \leq 40%	Exclusion from PPS
E01	Patient has a history of hypersensitivity to any of the study drugs, including history of hypersensitivity to drugs of similar chemical classes, or allergy to ACEis, ARBs, or NEP inhibitors as well as known or suspected contraindications to the study drugs	Exclusion from PPS
E02	Patient has history of intolerance to sacubitril and valsartan, ACEi or ARB standard of care doses	Exclusion from PPS
E03	Patient has history of angioedema	Exclusion from PPS
E04	Patient requires treatment with both ACE inhibitor and ARB	Exclusion from PPS

Deviation ID	Description of Deviation	Exclusion in Analyses
E12	Patient had a persistent or permanent atrial fibrillation at Screening/Baseline (Visit 1)	Exclusion from PPS
E13	Patient had Acute coronary syndrome, stroke, transient ischemic attack, cardiac, carotid or other major CV surgery, percutaneous coronary intervention (PCI) or carotid angioplasty within the 3 months prior to first Screening/Baseline (Visit 1)	Exclusion from PPS
E14	Patient has an Implantation of a cardiac resynchronization therapy pacemaker (CRT-P) or a cardiac resynchronization therapy defibrillator (CRT-D) or upgrading of an existing conventional pacemaker or an implantable cardioverter defibrillator (ICD) to CRT device within 3 months prior to first visit or intent to implant such a device	Exclusion from PPS
E15	Patient has a heart transplant or ventricular assistance device (VAD) or intent to transplant (on transplant list) or implant a VAD	Exclusion from PPS
E16	Patient has a Coronary or carotid artery disease likely to require surgical or percutaneous intervention within the 6 months after Visit 1	Exclusion from PPS
E17	Patient has a hemodynamically significant aortic stenosis/regurgitation or mitral valve disease other than mitral valve regurgitation related to LV dilation	Exclusion from PPS

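### SAP 5.4.1 narrows the protocol's notable low-SBP definition without declaring it, leaving the open-label phase with no count of SBP <90 mmHg alone

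*SAP*

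**What the plan says.** Protocol Appendix 1 states: "Clinically notable vital signs will be defined in this study as a SBP < 90 mmHg". It attaches no condition on change from baseline. Protocol 6.5.4 refers to that appendix for the definition. For analysis, Protocol 9.5.2 says: "Data from other tests (e.g., vital signs) will be listed, notable values will be flagged".

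SAP 5.4.1 gives the low-SBP criterion as "<90 mmHg and decrease of >20 mmHg from baseline", so both conditions must hold. SAP 2.8.4.1 applies the SAP 5.4.1 list in a table, by study phase and with unscheduled readings included, of patients "having notable vital signs based on changes relative to baseline values".

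The same SAP section also plans a second, separate summary: "The incidence of hypotension through Week 12 will be calculated by treatment group". Its criterion needs no fall: "Hypotension will be determined from the vital signs data as systolic blood pressure <90 mmHg". It reports a relative risk with a 95% confidence interval and also includes unscheduled readings.

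SAP Section 4, which records departures from the protocol analyses, lists the added hypotension summary. It even lists the removal of CPK from the notable chemistry list, which is another Appendix 1 item. It does not list the changed low-SBP rule.

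**The concern.** The same term, notable, carries two definitions, and nothing visible in the SAP tells the reader that the report uses a narrower one than the protocol. The effect is not spread evenly. The added condition can remove only patients whose baseline is already close to the threshold, and eligibility admits treated patients from just above 105 mmHg.

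The SBP <90 mmHg summary stops at Week 12. After that, everyone who continues receives sacubitril/valsartan, including those switching from enalapril. Hypotension is one of the three major risks named in Protocol 3.6.1, and the only one of those three described as an exception to similar rates in the earlier outcome trial (17.61% on sacubitril/valsartan, 11.97% on enalapril). At stake is whether the report contains an open-label count of low SBP that matches the protocol's own definition. For the double-blind phase, two tables may also show different low-SBP counts with no explanation.

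**Working it through.** The documents give no figure that depends on this definition, so there is nothing to reproduce. The check is to find where the two rules disagree.

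Inputs:
- Protocol rule (Appendix 1): reading r < 90.
- SAP rule (5.4.1): r < 90 and B − r > 20, where B is the baseline.
- Baseline (SAP 2.1.1): "baseline is defined as the last non-missing assessment prior to or on the start date of study treatment", unscheduled values excluded.
- Lowest eligible baseline: "SBP > 105 mm Hg on antihypertensive medication" (deviation I03 in SAP 5.6, matching Protocol 4.1, required at both screening and pre-randomization), or at least 140 mmHg if untreated.
- Assumption: SBP is recorded in whole mmHg, so the lowest eligible baseline is 106.

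The rules disagree when r < 90 but B − r ≤ 20, that is, when B − 20 ≤ r ≤ 89. In whole numbers this range is empty once B − 20 > 89, that is, from B = 110 upward.

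| Baseline | SAP rule met only if reading is | Readings <90 not counted |
|---|---|---|
| 106 | ≤ 106 − 21 = 85 | 86, 87, 88, 89 |
| 107 | ≤ 107 − 21 = 86 | 87, 88, 89 |
| 108 | ≤ 108 − 21 = 87 | 88, 89 |
| 109 | ≤ 109 − 21 = 88 | 89 |
| ≥ 110 | ≤ 89 | none |

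Eligible untreated patients start at 140 or above, so the rules always agree for them. Patients enrolled in deviation of the SBP criterion stay in the Safety Set if dosed, since I03 excludes only from the Per-Protocol Set. For them the gap is wider: at a baseline of 104, readings of 84–89 are not counted.

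These are readings, not patients. The table counts a patient once for any qualifying reading in the phase. A patient at baseline 106 with one reading of 87 and another of 85 is still counted. A patient is lost only if every reading below 90 falls in the last column.

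Coverage of low SBP by study phase:
- Double-blind: the notable table (narrower rule) and the SBP <90 mmHg incidence (protocol threshold).
- Open-label: the notable table (narrower rule) only, as far as threshold-based counts from vital signs go.

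**The case against.** A reader might infer that low-baseline patients with hypotension are missed altogether, or that the between-drug comparison is distorted. The documents do not support either. The Week 12 incidence in SAP 2.8.4.1 uses SBP <90 mmHg alone, by arm, so every randomized-phase reading in the table above counts there. The 17.61% against 11.97% contrast is between drugs, and in this trial that contrast exists only in the double-blind phase. The open-label phase has no comparator to distort.

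Nor is the open-label phase blind to hypotension. Treatment-emergent adverse events are summarized by study phase (SAP 2.8.1.2), SBP is summarized at each visit with minimum and quartiles, and all data are listed, so any reading below 90 can be recovered.

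The SAP rule may also be a deliberate convention. It uses the same absolute-plus-change form for high SBP, diastolic pressure and pulse, none of which Appendix 1 covers. Appendix 1 also serves as a site alert, and for analysis the protocol promises only listing and flagging, not an open-label incidence table.

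All of this stands, and it limits the point to one descriptive table. It does not remove the point. A deliberate convention that departs from a written protocol definition belongs in Section 4, and listings are not a count.

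**Conclusion.** The point holds in limited form. The two definitions conflict and the SAP does not declare the change. The notable vital signs table can undercount patients with baselines of 106–109 mmHg whose readings below 90 all lie within 20 mmHg of baseline. The practical loss is that the open-label phase has no SBP <90 mmHg count matching the protocol.

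No efficacy result changes, and neither does the randomized SBP <90 mmHg comparison through Week 12. The documents give no baseline SBP distribution, so the number of patients cannot be derived; the affected band is narrow. The result assumes whole-number readings and baselines that meet the eligibility criterion, and the band widens for patients enrolled in deviation of it. This is a minor reporting point.

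**What to change.** Reconcile Protocol Appendix 1 and SAP 5.4.1 for reporting:

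- Add an SBP <90 mmHg row, the protocol definition, to the notable vital signs table for both study phases. Keep the absolute-plus-change row beside it if that convention is wanted.
- List the SAP 5.4.1 rule in SAP Section 4 as a change from the protocol, with its reason. Listing it alone would settle the undeclared difference but leave the open-label gap.

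The cost is one extra table row and one line in Section 4, with no new data collection. Reported low-SBP counts may be slightly higher. The change concerns tabulation only and proposes no clinical threshold or action.
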